6.3 Cost-effectiveness

The health economic evaluation will be performed according to the Dutch Health Care Institute pharmacoeconomic guidelines.²¹

6.4 Software

Analysis of primary and secondary endpoints will be performed with SAS (SAS Institute Inc., Cary, NC, USA) or R software (R Core Team, Vienna, Austria). Multiple imputation will be performed in R software with the MICE package.²² Results from the imputation will be exported as imputed datasets in a format that will allow subsequent analysis in SAS. Some graphical representations and

descriptive tables may be constructed with SPSS (IBM Corp. IBM SPSS Statistics for Windows, Armonk, NY: IBM Corp). For any software or R package, the most recent available version will be used.

7. Missing data

Missing data will be minimised as we will use centralised data acquisition (eCRF) for all participating centres. This will be coordinated by the UMC Utrecht with appropriate monitoring on data queries. Missing data may nevertheless be unavoidable and may subsequently result in biased results.

7.1 Baseline variables

Multiple imputation will be applied for missing values on baseline variables that may be used in any of the statistical analyses. Prior to the imputation, an analysis will be conducted to evaluate associations between the occurrence of missing values and available patient and disease characteristics.

Multiple imputation will be applied with a fully conditional specification and performed for control groups and intervention groups separately,²³ with a correction for clustering in centers of inclusion. Initial imputations will be performed on data in a so-called wide format, where all measurements over time are included as separate variables. The logistic regression approach will be used for categorical variables, continuous measurements will be imputed with predictive mean matching. The imputation of baseline variables will be performed on all variables that will be included in the statistical analysis including primary and secondary outcomes at baseline and at follow-up. Additionally, other observed variables considered to be associated with missing values will be included in the imputation. The number of imputations will initially be equal to the percentage of patients with missing data on variables to be included in any analysis plus 10. When this percentage is below 10%, a minimum of 20 imputations will be used. When the percentage of patients with missing patients is larger than 50%, the number of imputations will be increased to 100.^{24,25}

7.2 Missing primary and secondary outcome measurements

A blinded sensor is used for measuring the primary endpoint. Patients with at least 168 hours of sensor data on a specific follow-up time will be included in the analyses. All valid TIR measurements at a specific time point during follow-up will be included in the analysis, also for patients with incomplete follow-up. Sensitivity analyses on the primary endpoint will be conducted to assess the impact of incomplete sensor measurements. Based on the consensus statement on glucose sensor measurement,⁷ analyses will be repeated by calculating the TIR based on the first 235.2 hours (i.e. 70% of 14 days) of sensor measurements for all patients, excluding patients with less than 235.2 hours of sensor data.

Even though primary and secondary outcomes will be included in the imputation of baseline variables, the imputed values of outcomes will not be included in the primary analysis, as this may result in biased estimation of treatment effect or loss of efficiency.^{24,26} For patients with missing outcomes due to intolerability of the DHFCL, a separate imputation and sensitivity analyses of primary and secondary outcomes is specified in the section on drop-outs (section 7.3). In these sensitivity analyses, imputed outcomes will be included. Patients with incomplete baseline variables that drop-out early after randomisation (i.e. prior to the measurement at 3 months) may be fully excluded.

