4.4 Definitions safety parameters

Safety parameters include AEs, SAEs and device-related issues.

AEs are defined as any undesirable experience occurring to a subject during the study, whether or not considered related to the DHFCL. AEs of special interest include:

- Events possibly related to glucagon or fluctuating glucose levels: nausea/fatigue/headache/restlessness;
- Skin reaction tape infusion set: erythema/discomfort/irritation/rash;
- Reaction infusion set/site: discomfort/inflammation/pain/lipodystrophy;
- Skin reaction tape glucose sensor: erythema/discomfort/irritation/rash/ damage;
- Reaction glucose sensor (insertion site): bruising/bleeding/pain.
- New diabetes complications;
- Deterioration (from baseline) of diabetes complications;
- Ketoacidosis;
- Severe hypoglycaemia (hypoglycaemia that leads to a seizure or unconsciousness),

Hypoglycaemia is a disease specific endpoint, and not recorded as AE in this trial.

SAEs are defined as any untoward medical occurrence or effect that

- results in death;
- is life threatening (at the time of the event);
- requires hospitalisation or prolongation of existing inpatients' hospitalisation;
- results in persistent or significant disability or incapacity;
- is a congenital anomaly or birth defect; or
- any other important medical event that did not result in any of the outcomes listed above due to medical or surgical intervention but could have been based upon appropriate judgement by the investigator.

An elective hospital admission will not be considered as a SAE.

Device incidents are defined as any malfunction or deterioration in the characteristics or performance of the DHFCL system, including use-error due to ergonomic features, as well as any inadequacy in the information supplied by the manufacturer and any undesirable side-effect.

5. Analysis datasets and statistical analyses

The primary and secondary analyses will be performed on an intention-to-treat (ITT) principle and per-protocol (PP) principle. All randomized participants will be analyzed for the ITT analysis and all safety analyses.

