7.3 Drop-outs due to intolerability of the DHFCL

7.3.1 Intolerability and lost to follow-up

A potential bias may occur in both ITT and PP analyses when a substantial number of patients do not follow the index treatment regime due to intolerability of the DHFCL. This is of special concern when these patients completely withdraw from the study and do not participate in follow-up measurements. When this occurs in more than 6 patients in arm 1 or more than 3 patients in arm 2 (to be decided separately for each arm), a separate sensitivity analysis will be performed. For these patients, we assume a return to the treatment-as-usual (comparable to the control group), missing outcomes of these patients will be imputed based on an imputation model that is estimated in the control group only.²⁷ Further specifications of the multiple imputation will be applied as described above. For this specific sensitivity analysis, missing outcomes of patients who drop out for other reasons will be included in the analysis, yet based on the imputation in the group they were randomised in.

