The second analysis aims to evaluate the treatment effect in the principal stratum of patients that tolerate and fully adhere to DHFCL. This analysis is performed in two steps. In the first step, data from patients randomised to the intervention group are used to construct a propensity score (PS) model for discontinuation due to intolerability of the DHFCL. In the second step, the analysis as described in section 6.1 is performed with weights based on the propensity scores. The propensity score will be constructed with logistic regression with intolerability (yes/no) as outcome variable in the intervention groups only. The model will include patient characteristics and

variables related to diabetes status measured at baseline. Patient characteristics include age, sex, educational level. Diabetes-related variables include TIR, duration of diabetes and patient reported daily insulin use. Variables to be included in the PS model may be subject to change based on available numbers (e.g. the number of discontinuing patients and valid observations for baseline variables) and clinical information on reasons for discontinuation. Outcomes and other variables measured during follow-up will not be included in the PS model.

The PS model will be used to estimate predicted probabilities of discontinuation due to intolerability for patients in the control group, these probabilities will be used as weights. Weights will only be applied in the control group. In the intervention group only two weights will be applied: a weight of 0 for patients who discontinued due to intolerability (i.e. effectively excluding these patients from the analysis) and a weight of 1 for all others. The weight will be applied for the analysis as described in section $6.1.^{28}$

8. Safety analyses

All safety outcomes will be presented for all events from baseline to final visit. Analyses will have a similar approach as with the secondary endpoints in the case of sufficient numbers of events.

9. Planned interim analyses

A formal interim analysis for primary and secondary outcomes is not planned. A Data Safety Monitoring Board will be established to monitor (S)AEs.

10. Subgroup analyses

In exploratory analyses, the primary and key secondary outcomes will be assessed separately for interaction with certain baseline variables as described below.

Subgroup analyses will assess the effectiveness of the DHFCL by the following patient characteristics:

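### Section 7.2 permits an unscoped, discretionary exclusion of early drop-outs with incomplete baseline data, which conflicts with sections 7.1 and 7.3.1

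*SAP*

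**What the plan says.** SAP section 7.2, on missing outcome measurements, ends with a rule that patients with incomplete baseline variables who "drop-out early after randomisation (i.e. prior to the measurement at 3 months) may be fully excluded". The sentence directly before it concerns the drop-out analyses of section 7.3: "In these sensitivity analyses, imputed outcomes will be included". The rule makes no exception for those analyses. It does not say which baseline variables count, who decides, or when.

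Four other parts of the SAP bear on the same patients:

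- Section 7.1: "Multiple imputation will be applied for missing values on baseline variables that may be used in any of the statistical analyses".
- Section 7.3.1 is written for DHFCL-intolerant patients, with special concern for those who "completely withdraw from the study and do not participate in follow-up measurements". Above 6 such patients in arm 1, or above 3 in arm 2, their outcomes are imputed from a model fitted in the control group. Patients who drop out for other reasons are also kept, with imputation within their randomised group.
- Section 5.1 limits the primary analysis to patients with enough blinded sensor data at baseline and at one or more follow-up visits.
- Section 5: "All randomized participants will be analyzed for the ITT analysis and all safety analyses". Section 8 adds: "All safety outcomes will be presented for all events from baseline to final visit".

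**The concern.** The exclusion depends on an event after randomisation, in an open-label trial, and is optional. It therefore leaves a choice that could be made once outcomes are known.

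It also has little to do in the primary analysis, where a patient who leaves before month 3 contributes no outcome anyway. Its practical effect falls mainly on the analyses that impute outcomes, above all 7.3.1. A DHFCL patient who cannot tolerate the system and leaves before the first follow-up measurement is the clearest case for that analysis. Dropping such patients brings back the selection that 7.3.1 was written to examine.

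The baseline condition can easily be met. Section 5.1 sets baseline sensor metrics to missing below 168 hours of data, and baseline TIR is a covariate in the adjusted model of section 6.1. A short baseline sensor wear could be enough to make a patient incomplete.

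**Working it through.** **1. Does the sentence change the primary analysis?** Section 5.1 requires follow-up sensor data, and the model in section 6.1 uses TIR at 3, 6, 9 and 12 months. A patient who leaves before month 3 has none of these. The primary estimate is essentially the same with or without the rule.

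**2. Is the exclusion needed because baseline data are missing?** No. Section 7.1 already imputes missing baseline values for variables used in any analysis.

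**3. Does it fit with 7.3.1?** No. For the same patient (no follow-up, incomplete baseline), 7.3.1 says outcomes will be imputed and analysed, while 7.2 says the patient may be left out altogether. Nothing states which rule prevails.

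**4. How large could the effect on 7.3.1 be?** The SAP gives no figure for this, so there is none to reproduce. The illustration uses the planning values in sections 3.1 and 3.2:

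- Arm 1: difference d = 85 − 78 = 7 points, N = 85 index patients, smallest triggering count k = 7 (7/85 = 8.2%).
- Arm 2: d = 85 − 70 = 15 points, N = 35, k = 4 (4/35 = 11.4%).

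Assumptions: all k intolerant patients leave before month 3; their imputed mean equals the control mean; the other index patients have the full planning effect. If x of the k are excluded because of incomplete baseline data, the expected 7.3.1 estimate is d × (N − k)/(N − x).

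| Arm | x excluded | Calculation | Estimate | Shift from x = 0 |
|---|---|---|---|---|
| 1 | 0 | 7 × 78/85 | 6.42 | – |
| 1 | 1 | 7 × 78/84 | 6.50 | 0.08 |
| 1 | 3 | 7 × 78/82 | 6.66 | 0.24 |
| 1 | 7 | 7 × 78/78 | 7.00 | 0.58 |
| 2 | 0 | 15 × 31/35 | 13.29 | – |
| 2 | 1 | 15 × 31/34 | 13.68 | 0.39 |
| 2 | 2 | 15 × 31/33 | 14.09 | 0.81 |
| 2 | 4 | 15 × 31/31 | 15.00 | 1.71 |

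The x = k rows are the maximum shift for that count only. The trigger values are minimums, not caps on drop-out. With twice as many, keeping everyone gives 7 × 71/85 = 5.85 in arm 1 and 15 × 27/35 = 11.57 in arm 2, still against 7.0 and 15.0 if all are excluded.

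**5. What happens to the trigger?** The table assumes that excluded patients still count towards it. The SAP does not say. If they did not count, one exclusion would take 7 to 6 or 4 to 3, and 7.3.1 would not be run.

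**The case against.** The best defence is that the sentence only records a consequence of the paragraph it ends. That paragraph explains why imputed outcomes stay out of the primary analysis, and a patient with incomplete baseline data and no follow-up has little to analyse there. Section 7.3.1 then speaks more specifically and in mandatory terms, and carries over no exclusion. This is a reasonable reading and may be what the authors meant. But the sentence does not say so, it follows directly on the reference to the 7.3 analyses, and on this reading it adds nothing that section 5.1 does not already settle.

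The size is also fairly challenged. The illustration needs trigger-level intolerance, departure before month 3 and incomplete baseline data together. Section 7 plans central data capture with query monitoring. If 10% of these patients were incomplete (an assumption), the expected estimates would be 7 × 78/84.3 = 6.48 in arm 1 and 15 × 31/34.6 = 13.44 in arm 2, shifts of about 0.05 and 0.15 points. That stands: the effect may well be small.

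Four stronger readings might be inferred, and the SAP does not support them:

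- *That these patients leave the safety tables.* Section 7.2 is headed "7.2 Missing primary and secondary outcome measurements" and does not mention safety. Section 5 keeps all randomised participants in every safety analysis, and section 8 presents all events. The word 'fully' is at most a loose end to tidy.
- *That early DHFCL drop-outs as a class are removed.* The rule is permissive and also needs incomplete baseline data. Those with complete baselines stay in 7.3.1.
- *That one missing value on any baseline variable is enough.* The SAP leaves open which variables count.
- *That the exclusion applies to one group only.* It covers both. What is asymmetric is its effect in 7.3.1, since only index patients can be intolerant of the DHFCL.

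**Conclusion.** The point holds as an internal conflict and an unscoped permission. Section 7.2 allows the removal of patients whose baseline values section 7.1 imputes and whose outcomes section 7.3.1 says will be imputed and analysed. No criterion or timing is given.

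The primary estimate and its p-value are essentially unaffected. The consequence lies mainly in a conditional sensitivity analysis, where the direction is clear: excluding intolerant patients moves the estimate towards the effect in those who tolerated the device. At the smallest triggering counts the shift is at most about 0.6 points in arm 1 and 1.7 points in arm 2. Both figures rest on the planning means and on every such patient having incomplete baseline data. The effect on the trigger is conditional, because the SAP is silent on whether excluded patients are counted. A loss of safety data is not established.

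**What to change.** Delete the last sentence of section 7.2, or replace it with:

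*Patients without any valid follow-up measurement contribute no outcome to the main mixed model. They remain in the 7.3.1 count and imputation, with missing baseline values imputed as in 7.1; safety analyses include all randomised participants as stated in section 5.*

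This changes one sentence and needs no new data. The only added work is a few more imputed records in a sensitivity analysis. It should be settled before outcome data are examined by group.

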7.3 Drop-outs due to intolerability of the DHFCL

7.3.1 Intolerability and lost to follow-up

A potential bias may occur in both ITT and PP analyses when a substantial number of patients do not follow the index treatment regime due to intolerability of the DHFCL. This is of special concern when these patients completely withdraw from the study and do not participate in follow-up measurements. When this occurs in more than 6 patients in arm 1 or more than 3 patients in arm 2 (to be decided separately for each arm), a separate sensitivity analysis will be performed. For these patients, we assume a return to the treatment-as-usual (comparable to the control group), missing outcomes of these patients will be imputed based on an imputation model that is estimated in the control group only.²⁷ Further specifications of the multiple imputation will be applied as described above. For this specific sensitivity analysis, missing outcomes of patients who drop out for other reasons will be included in the analysis, yet based on the imputation in the group they were randomised in.

7.3.2 Intolerability and continuation of study measurements

Intolerability of the DHFCL is also of concern for patients who discontinue treatment while continuing with the study. Follow-up measurements in these patients will be performed as planned, and these measurements will be included in the ITT analysis as described in section 6.1. The treatment effect derived from the ITT analysis, while being of primary interest for decision making, will not represent the full treatment potential of the DHFCL. Results of the PP analysis may be biased, as balance between treatment groups after randomisation may be lost. To further evaluate the beneficial effect of the DHFCL, two additional sensitivity analyses will be performed.

The first analysis aims to evaluate the treatment effect under a hypothetical scenario where all patients were treated with the DHFCL and were fully adherent. Initially, observations of the outcome after treatment discontinuation or non-adherence will be excluded from the analysis and set to missing. Subsequently, multiple imputation will be used to impute these outcomes. Multiple imputation will be applied as described in section 7.1, inclusion of additional variables in the imputation model will be considered based on clinical literature as well as observed patterns of missing data and discontinuation. As described in section 7.1, imputations will be performed for each arm and each treatment group separately. Analysis of the primary outcome will be performed as described in section 6.1. In an additional step, all follow-up outcomes, both prior to or after discontinuation or non-adherence, will be set to missing and imputed. Again, the resulting imputed data will be analysed as described in section 6.1. It should be noted that imputations described in this section will be performed separately from imputations described in sections 7.1.

The second analysis aims to evaluate the treatment effect in the principal stratum of patients that tolerate and fully adhere to DHFCL. This analysis is performed in two steps. In the first step, data from patients randomised to the intervention group are used to construct a propensity score (PS) model for discontinuation due to intolerability of the DHFCL. In the second step, the analysis as described in section 6.1 is performed with weights based on the propensity scores. The propensity score will be constructed with logistic regression with intolerability (yes/no) as outcome variable in the intervention groups only. The model will include patient characteristics and

variables related to diabetes status measured at baseline. Patient characteristics include age, sex, educational level. Diabetes-related variables include TIR, duration of diabetes and patient reported daily insulin use. Variables to be included in the PS model may be subject to change based on available numbers (e.g. the number of discontinuing patients and valid observations for baseline variables) and clinical information on reasons for discontinuation. Outcomes and other variables measured during follow-up will not be included in the PS model.

The PS model will be used to estimate predicted probabilities of discontinuation due to intolerability for patients in the control group, these probabilities will be used as weights. Weights will only be applied in the control group. In the intervention group only two weights will be applied: a weight of 0 for patients who discontinued due to intolerability (i.e. effectively excluding these patients from the analysis) and a weight of 1 for all others. The weight will be applied for the analysis as described in section $6.1.^{28}$

8. Safety analyses

All safety outcomes will be presented for all events from baseline to final visit. Analyses will have a similar approach as with the secondary endpoints in the case of sufficient numbers of events.

9. Planned interim analyses

A formal interim analysis for primary and secondary outcomes is not planned. A Data Safety Monitoring Board will be established to monitor (S)AEs.

10. Subgroup analyses

In exploratory analyses, the primary and key secondary outcomes will be assessed separately for interaction with certain baseline variables as described below.

Subgroup analyses will assess the effectiveness of the DHFCL by the following patient characteristics:

- Age groups (18 to <30 years old, 30 to <50 years old, ≥50 to 75 years old)
- Sex
- Baseline HbA1c (<53 mmol/mol, 53 to <64 mmol/mol, 64 to <75 mmol/mol, ≥75 mmol/mol)
- Type 1 diabetes duration (<5 years; 5 to <10 years; 10 to <20 years; ≥20 years)
- Body mass index subgroups as follows:
 - \circ Underweight BMI <18.5 kg/m²
 - \circ Normal weight BMI 18.5 to <24.9 kg/m²
 - Overweight BMI ≥25 kg/m²
- Education (low [no education, primary education or lower vocational education], middle [general secondary education, general vocational education, higher secondary and pre-university education], and high [higher vocational education and university])
- rtCGM or FGM use prior to enrollment (MDI group only)

Effect sizes and 95% confidence intervals will be presented per subgroup in a forest plot. Interpretation of the subgroup analyses will be made with caution, particularly if the primary analysis is not significant.

11. Exploratory analyses

No exploratory analyses are planned.

12. References

- Bergenstal, R. M., Nimri, R., Beck, R. W., Criego, A., Laffel, L., Schatz, D. FSG. A Comparison of Two Hybrid Closed-Loop Systems in Adolescents and Young Adults with Type 1 Diabetes: A Multicenter Randomised Crossover Trial. Lancet. 2021;397(10270):208–19.
- Brown, S. A., Kovatchev, B. P., Raghinaru, D., Lum, J. W., Buckingham, B. A., Kudva, Y. C., ... & Beck RW. Six-Month Randomized, Multicenter Trial of Closed-Loop Control in Type 1 Diabetes. New England Journal of Medicine. 2019;381(18):1707–17.

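### The principal-stratum analysis in SAP 7.3.2 is named for patients who tolerate and adhere, but its score model and weights select on intolerability alone

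*SAP*

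**What the plan says.** Section 7.3.2 of the SAP adds two sensitivity analyses for patients who stop DHFCL but stay in the study. The second is said to address the "principal stratum of patients that tolerate and fully adhere to DHFCL". Its steps are:

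- The first step builds a "propensity score (PS) model for discontinuation due to intolerability of the DHFCL", fitted as a "logistic regression with intolerability (yes/no) as outcome variable in the intervention groups only".
- In the DHFCL group the weights are "a weight of 0 for patients who discontinued due to intolerability" "and a weight of 1 for all others".
- In the control group the same model supplies "predicted probabilities of discontinuation due to intolerability for patients in the control group, these probabilities will be used as weights".

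The first analysis in the same section addresses full adherence by hypothetical imputation. There, "observations of the outcome after treatment discontinuation or non-adherence will be excluded from the analysis and set to missing".

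**The concern.** The named stratum has two conditions, tolerating DHFCL and adhering fully to it. Only the first enters the calculation. A DHFCL patient who stopped for some other reason, or who stayed on the system with the loop often inactive, has weight 1 and contributes outcomes measured off treatment or under partial treatment. On the control side, the score carries no information about who would have adhered.

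What is at stake is what the analysis may be reported to show. Section 7.3.2 introduces both analyses because the ITT effect does not show what DHFCL can achieve when it is used as intended. A reader would be told that the second result applies to fully adherent patients when it does not. The two analyses would also treat non-adherence in opposite ways, one removing the affected outcomes and the other keeping them. Part of any difference between their results could come from that inconsistency.

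**Working it through.** **Step 1: can intolerability be read to include non-adherence?** The SAP keeps the two apart.

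- Section 7.3.2, first analysis: discontinuation and non-adherence are listed as two events, neither limited to intolerability.
- Section 7.3.1: patients who drop out for reasons other than intolerability are imputed differently from those who drop out because of it.
- Section 5: the per-protocol set has its own adherence criterion, closed loop active for at least 80% of the time.
- Section 4.3: reasons for stopping DHFCL are an endpoint, so several reasons are expected.

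**Step 2: does the stated flexibility close the gap?** "Variables to be included in the PS model may be subject to change based on available numbers" follows the list of baseline covariates and concerns those. It leaves the score outcome and the 0/1 rule as they are.

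The written rule and the named stratum therefore coincide only if no tolerant DHFCL patient is non-adherent or stops for another reason.

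**Step 3: planning figures used for illustration (sections 3.1 and 3.2).** Arm 1 assumes 78% (SD 17) against 85% (SD 4), a difference of 7 points. Arm 2 assumes 70% (SD 20) against 85% (SD 4), a difference of 15 points. With an unequal-variance t-test at two-sided 0.05, the smallest n per group with at least 90% power is 68 in arm 1 (power 90.4%) and 22 in arm 2 (power 91.0%). Both match the SAP.

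**Step 4: dilution, if the control weights correctly represented tolerators.** Let Δ be the effect in patients who tolerate and adhere. Let f be the share of weight-1 DHFCL patients who do not adhere, and assume they have no benefit at all. The contrast is then (1 − f) × Δ.

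| f (assumed) | Arm 1, Δ = 7 | Arm 2, Δ = 15 |
|---|---|---|
| 5% | 0.95 × 7 = 6.65 | 0.95 × 15 = 14.25 |
| 10% | 0.90 × 7 = 6.30 | 0.90 × 15 = 13.50 |
| 15% | 0.85 × 7 = 5.95 | 0.85 × 15 = 12.75 |

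The same can be written with shares of all DHFCL patients: Δ × (1 − pI − pN)/(1 − pI), where pI is the intolerant share and pN the tolerant but non-adherent share. With pI = 10% and pN = 5%, 10% or 20% (all assumed):

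- Arm 1: 7 × 0.85/0.90 = 6.6, 7 × 0.80/0.90 = 6.2, 7 × 0.70/0.90 = 5.4.
- Arm 2: 15 × 0.85/0.90 = 14.2, 15 × 0.80/0.90 = 13.3, 15 × 0.70/0.90 = 11.7.

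**Step 5: interaction with the control weights.** A large-sample simulation for arm 1 assumed about 11% intolerant and 11% tolerant but non-adherent patients. Both were more frequent with a worse baseline, and neither had any benefit. The true effect in those who tolerate and adhere was 7.0.

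- Intolerability-only rule, controls weighted by the probability of not stopping: 6.15.
- Membership defined by both conditions, controls weighted by the probability of membership: 7.0.
- Intolerability-only rule, controls weighted as the SAP states, by the probability of stopping: 13.4.

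The first two lines show that the adherence mismatch remains after the control weights are turned round. The third shows that the control weights as written can outweigh it and act in the opposite direction.

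**The case against.** The best case for the plan is that this is mainly a label. Sections 7.3 and 7.3.2 are headed by intolerability, and the score model and all the weights use that one event. The rule for who gets which weight leaves the analyst no discretion. Only the adherence part of the stratum's name does not fit, and renaming resolves it. This stands, and it is why renaming is a full remedy.

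A reader might go further and infer that the reported estimate will be too small. The documents do not support that. The direction holds only if the control weights target tolerators, and section 7.3.2 weights controls by the probability of discontinuing.

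The sizes in Step 4 are also a worst case. They give every non-adherent patient TIR like a control, yet a patient with the loop active 75% of the time fails the 80% criterion and would plausibly keep some benefit. The 7 and 15 points are planning differences for the randomised comparison, not stated effects among adherers. The shifts of 0.35 to 1.05 and 0.75 to 2.25 points are small beside the approximate 95% CI half-widths at full enrolment: 1.96 × √((17² + 4²)/85) = 3.7 points in arm 1 and 1.96 × √((20² + 4²)/35) = 6.8 points in arm 2.

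The two analyses in 7.3.2 also differ in population by design, so they need not agree even after correction. That does not justify handling non-adherence differently without saying so.

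**Conclusion.** The point holds as a mismatch between the stratum that section 7.3.2 names and the membership rule it specifies. Followed exactly, the rule selects at best patients who would not discontinue DHFCL because of intolerability.

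The SAP gives neither the size nor the direction of the consequence. The downward shifts to 6.65–5.95 points in arm 1 and 14.25–12.75 in arm 2 rest on three assumptions: a non-adherent share of 5% to 15% among weight-1 patients, no benefit in any of them, and control weights that correctly represent tolerators. The last is not met as the text stands, so no direction can be claimed for the analysis as written.

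Only a supplementary sensitivity analysis is affected. The primary ITT comparison does not change. Correction is still worthwhile before analysis, because it determines what this result may be said to show.

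**What to change.** Use one membership definition throughout the second analysis in section 7.3.2, by either route:

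- **(a) Rename.** Call the stratum, and the conclusion drawn from it, patients who would not discontinue DHFCL because of intolerability. This needs wording only.
- **(b) Add adherence.** Define full adherence explicitly for each patient. Use tolerating and adhering together as both the score outcome and the 0/1 weight in the DHFCL group, and weight controls by the predicted probability of membership.

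For (b), the closed-loop criterion in section 5 is a natural source, and section 4.2.4 already provides for logged algorithm status. The new indicator should be stated as an adaptation and not presented as the per-protocol rule itself. That rule keeps a patient's visits up to a treatment change and adds a medication criterion, whereas a stratum indicator keeps or drops the whole patient.

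The cost of (b) is that a few more DHFCL patients get weight 0. Under (a), the direction of the control weights still has to be corrected as a separate matter.
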